7.8.2 Laboratory data

7.8.2.1 Laboratory data

The analyses of laboratory data will be descriptive in nature and will be based on BI standards [\(5\)](#). For both the phase Ib and the phase II part the on-treatment period as considered for the analysis of adverse events of the phase Ib part will be applied for laboratory values except for that the baseline laboratory value will be included in the 'on-treatment' period. Patients having at least one post-baseline laboratory value will be displayed in the descriptive analyses.

Descriptive statistics, including change from baseline and frequency of patients with transitions relative to the reference range, will be provided. CTCAE grades for applicable laboratory parameters will be calculated according to CTCAE version 4.03 ([R10-4848](#)). The following outputs will be presented:

- Worst CTCAE grade experienced during the on-treatment phase.
- Transitions of CTCAE grade from baseline to worst laboratory value, from worst to last laboratory value during the on-treatment phase, and from baseline to last laboratory value.

Patients with missing CTCAE grade at baseline or no baseline value but post baseline values will be displayed in the category "Missing CTCAE grade at baseline". Laboratory values without CTCAE grading will be compared to their reference ranges and frequency tables will be provided for the number of patients within and outside the reference range at baseline and the last measurement on treatment.

Analysis of potentially clinically significant abnormal laboratory values, and handling of CTCAE grade -1 and -9 laboratory parameters, are described in the SOP for "Display and analysis of laboratory data" [\(5\)](#), Reference Document 9.

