7.8.1 Adverse events

The analyses of AEs will be descriptive in nature. All analyses will be based on the number of patients with AEs (not the number of AEs).

Proprietary confidential information © 2018 Boehringer Ingelheim International GmbH or one or more of its affiliated companies

For analysis multiple AE occurrence data on the CRF will be collapsed into an AE event provided that all of the following applies:

- All AE attributes are identical (Lowest Level Term (LLT), Common Terminology Criteria for Adverse Events (CTCAE) grade, action taken with trial medication, therapy required, seriousness, reason for seriousness, relationship, outcome, AE of special interest)
- The occurrences were time-overlapping or time-adjacent (time-adjacency of 2 occurrences is given if the second occurrence started on the same day or on the day after the end of the first occurrence)

For further details on summarisation of AE data, please refer to [\(2\)](#) and [\(4\)](#).

Adverse events will be coded with the most recent version of MedDRA. The severity of AEs will be scaled according to CTCAE (CTCAE version 4.03 ([R10-4848](#))).

The analyses of AEs will be based on the concept of treatment-emergent AEs. For the phase Ib, that means that all AEs with an onset between first treatment administration until end of the REP will be assigned as 'on treatment'. All adverse events occurring before first drug intake will be assigned to 'screening' and all adverse events occurring after the REP will be assigned to 'post-treatment'; these AEs will be displayed in separate tables and listings. First drug intake includes the run-in period for Phase Ib part.

For the phase II part it has to be taken into consideration that the sponsor decided to stop treatment with xentuzumab on 28th of October 2016, but continued treatment with everolimus and exemestane. Therefore, the analysis of on-treatment AEs will be split in two parts:

1) AEs with onset date on or before 9th of December 2016

This includes the following patients:

- Patients of both arms who completed the REP on or before 9th of December 2016, i.e. AEs until the end of REP will be considered.
- Patients who stopped xentuzumab on 28th of October 2016 due to sponsor's decision, i.e. AEs with onset date on or before the 9th of December 2016 will be considered.
- Patients receiving everolimus and exemestane only, i.e. AEs with onset date on or before 9th of December 2016 will be considered.

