2) AEs with onset after 9th of December 2016

This includes the following patients:

- Patients who stopped xentuzumab on 28th of October 2016 due to sponsor's decision, i.e. AEs with onset date after 9th of December 2016 will be considered.
- Patients receiving everolimus and exemestane only, i.e. AEs with onset date after 9th of December 2016 will be considered.

Both parts will be analyzed by treatment and a total column will be given.

Proprietary confidential information © 2018 Boehringer Ingelheim International GmbH or one or more of its affiliated companies

For the Phase II part all AEs occurring before first drug intake will be assigned to 'screening' and all AEs occurring after the REP will be assigned as 'post-treatment'.

AEs will be displayed by the initial dose of study medication administered on the first day of treatment (or planned to be administered, for the run-in period of the Phase Ib part).

An overall summary of AEs will be presented. The frequency of patients with AEs will be summarised by treatment, primary system organ class (SOC) and preferred term (PT).

Separate tables will be provided for patients with drug-related AEs, AEs leading to dose reduction, AEs leading to discontinuation, serious adverse events (SAE), serious drug-related AEs, AEs leading to death, other significant AEs, adverse events of special interest (AESI), and AEs fulfilling the DLT definition (for phase Ib part only). For the Phase II part an overall summary of AEs as well as a table for AEs and SAEs by treatment will be provided for the subgroups of visceral involvement.

Sorting order:

In tables presenting SOC and PT, SOCs will be sorted alphabetically and PTs (within SOC) by descending frequency.

Reporting of CTCAE grades in tables:

In tables showing AEs by worst CTCAE grade, AEs with missing CTCAE grade will only be displayed under the category "All grades", but no category "Missing grade" will be displayed. Therefore the categories "Grade 1" to "Grade 5" might not add up to the category "All grades"; a footnote will explain this handling.

Displaying of CTCAE grades in AE tables (Section 15) will be "All grades", "Grade 1", "Grade 2", "Grade 3", "Grade 4", and "Grade 5" separately. In the appendix (Section 16.1.9.2), the categorisation "All grades", "Grade 1/2", "Grade 3/4/5", will be used.

Listings of AEs

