7.8.2.2 Laboratory values of special interest

Hepatic enzyme elevations (potential Hy's law cases):

These are defined as those cases where a combination of all of the following events occurred: any on-treatment value of Alanine Aminotransferase (ALT) and/or Aspartate Transaminase (AST) > 3 Upper Limit of Normal (ULN) with total bilirubin ≥ 2 ULN and Alkaline Phosphatase (ALKP) < 2 ULN. The events can occur in any order, but must occur within 14 days of the previous event, i.e. the second event must occur within 14 days of the first event, and the third event must occur within 14 days of the second event, etc.

Patients with missing laboratory values for liver enzymes will be excluded from these analyses but will be presented separately in a listing. Tabulations of hepatic enzyme elevations and liver laboratory values (see Section 5.2.2.1 of the CTP), including flags of true Drug-Induced Liver Injury (DILI) cases, are created in accordance with the Food and Drug Administration (FDA) DILI guidance ([P09-12413](#)).

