7.8.4 ECG

Newly emergent abnormalities will be recorded and analysed as AEs if judged clinically relevant by the investigator.

The ECG analyses will be performed using the ECG Set, except those concerning the relationship between plasma concentrations and ECG endpoints which will be based on the ECG-PK set. All analyses will be based on the centrally evaluated ECG data collected until the safety cut-off date of 9th December 2016. Centrally evaluated ECGs recorded after this date, will only be presented in listings.

Descriptive analyses (separate analysis of Phase Ib and Phase II parts)

Absolute values and change from baseline in QTcF interval, QT interval, heart rate, PR interval, and QRS complex will be summarized descriptively by initial treatment, cycle, day and planned time.

Frequency tables will be provided for all categorical endpoints including notable findings and qualitative ECG assessments. Frequencies of the increases in QTcF and QT intervals above thresholds such as 450 msec, 480 msec, and 500 msec between baseline and on-treatment values will be displayed in two-way shift tables by initial treatment.

Notable findings (occurring until the safety cut-off date) of patients in the TS who are excluded from the ECG Set will be listed in separate listings which will be presented in Section 15 of the CTR.

The QTcB interval as well as the percentage changes for PR interval and QRS complex will only be displayed in Listings (Appendix 16.2.8)

Additional statistical analyses will be performed for the Phase II part as described below:

Repeated measures analyses

The endpoint 'change in QTcF interval between baseline and on-treatment' will be analysed by a linear mixed-effects model for repeated measures (MMRM). This model will include the fixed, categorical effects of 'treatment' and 'timepoint', the 'treatment-by- timepoint' interaction, as well as the continuous, fixed covariate 'baseline' and the 'baseline-by- timepoint' interaction. An unstructured covariance structure will be used to model the within-patient measurements. The SAS® procedure MIXED will be used, involving the restricted maximum likelihood estimation method, and the Kenward-Roger method will be applied to adjust standard errors and estimate denominator degrees of freedom. The model is detailed in [Section 9.2.2](#).

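### Phase II laboratory outputs have no 9 December 2016 boundary, unlike adverse events and ECGs, and the stand-alone worst-grade table counts the pre-treatment value as on-treatment

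*SAP*

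**What the plan says.** SAP 7.8.2.1 sets one window for laboratory data in both parts of the trial: "the on-treatment period as considered for the analysis of adverse events of the phase Ib part will be applied for laboratory values". In SAP 7.8.1 that phase Ib period starts at the first administration and ends with the residual effect period (REP). SAP 6.1 gives the REP as 42 days. No calendar date is attached. SAP 7.8.2.1 then makes one exception: "the baseline laboratory value will be included in the" on-treatment period.

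The outputs built on this window are "Worst CTCAE grade experienced during the on-treatment phase" and three transition tables: baseline to worst, worst to last, and baseline to last. On who is shown: "Patients having at least one post-baseline laboratory value will be displayed in the descriptive analyses".

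Other phase II safety data are handled differently. SAP 7.8.1 notes that xentuzumab was stopped on 28 October 2016 while everolimus and exemestane went on, and continues: "Therefore, the analysis of on-treatment AEs will be split in two parts". The second part covers, among others, patients taken off xentuzumab by the sponsor, for whom "AEs with onset date after 9th of December 2016 will be considered". For ECGs, SAP 7.8.4 states: "All analyses will be based on the centrally evaluated ECG data collected until the safety cut-off date of 9th December 2016". Later ECGs are only listed.

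**The concern.** The reason given for splitting adverse events applies equally to laboratory values. After 28 October 2016 an arm 2 patient could remain on everolimus and exemestane alone. A laboratory value taken months later would still be tabulated under the xentuzumab arm, and could be the value reported as worst or last. Protocol 2.3 lists hyperglycaemia and hyperlipidaemia among everolimus class effects, and everolimus is one of the drugs that continued. What is lost is attribution: a grade shown for the triplet may have arisen well after xentuzumab stopped. A reader of the adverse event tables up to 9 December 2016 would also find no graded laboratory table for the same period.

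The baseline rule is a separate problem of labelling. A table headed as on-treatment should not report a grade measured before any study drug was given.

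**Working it through.** **Step 1: the cut-off date.** SAP 6.3 derives it as the end of xentuzumab plus the REP. 28 October 2016 + 42 days (3 in October, 30 in November, 9 in December) = 9 December 2016. This agrees with the plan.

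**Step 2: the three data types side by side (phase II).**

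| Data | Window | 9 December 2016 used? | Baseline inside on-treatment? |
|---|---|---|---|
| Adverse events (SAP 7, 7.8.1) | First dose to end of REP | Yes, split | No; events before first dose are assigned to screening |
| ECG (SAP 5.4.6, 7.8.4, 9.2.5) | After first dose to end of REP | Yes, cut; later ECGs listed | No |
| Laboratory (SAP 7.8.2.1) | First dose to end of REP | No | Yes |

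**Step 3: which dose starts the REP.** The SAP gives a length and no explicit start, and SAP 6.1 refers study periods to a separate document that is not supplied. The supplied text best supports the last dose of any trial drug:
- SAP 3 uses study medication for any of the drugs, alone or combined.
- SAP 5.4.2 runs treatment duration to the last dose of any of them.
- SAP 7.8.1 speaks of the REP for both arms, and arm 1 never receives xentuzumab.
- SAP 7.8.1 keeps events after 9 December 2016 in sponsor-stopped patients inside the on-treatment analysis.

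On this reading both arms follow one rule, and arm 2 windows can extend past 9 December 2016 on the doublet alone.

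**Step 4: whether such time exists.** SAP 4.2 has the report written before all patients are off trial medication. SAP Table 6.6: 1 sets end of treatment for ongoing patients to the snapshot or database lock. SAP 7.8.1 has an adverse event part after the cut-off. The lock date is not given. Purely as calendar distance, 9 December 2016 to the 3 May 2017 SAP version is 145 days (5 full 28-day courses), and to the 25 April 2018 version 502 days (17 full courses). Neither figure is a count of laboratory samples.

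**Step 5: effect of including baseline.** Let g0 be the baseline grade and g1 the worst post-baseline grade, each 0 to 4. With baseline included, the table reports m = max(g0, g1). There are 5 × 5 = 25 possible pairs:
- g1 > g0: 10 pairs; m = g1, worsening.
- g1 = g0: 5 pairs; no difference.
- g1 < g0: 10 pairs; m = g0, so the pre-treatment grade is displayed.

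Since m > g0 exactly when g1 > g0, the number of patients who worsen in the baseline-to-worst table is the same either way. The stand-alone table and the worst in the worst-to-last table do change, in the last 10 pairs. Last values are unaffected by this rule, because every displayed patient has a post-baseline value.

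**Step 6: illustration only.** The documents give no grade frequencies. Assume a share b of patients with baseline grade 1 or more, a share p with post-baseline worst grade 1 or more, and independence. The tabulated share becomes 1 − (1 − p)(1 − b), a rise of b(1 − p):
- b = 5%, p = 80%: 0.05 × 0.20 = 1 percentage point.
- b = 10%, p = 50%: 0.10 × 0.50 = 5 points (50% becomes 55%).
- b = 20%, p = 20%: 0.20 × 0.80 = 16 points.

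If abnormal baselines tend to persist, independence overstates the rise.

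**The case against.** The strongest reply is that SAP 7.8.2.1 is a deliberate rule. It names both parts of the trial and picks the phase Ib period in the same document that splits phase II adverse events. The company laboratory SOP, amendment 3 and the study-periods document are cited but not supplied, and any of them could contain a limit. Continued treatment does not prove that laboratory values after 9 December 2016 are in the database. Clinically relevant laboratory changes, hepatic-injury events of special interest and the user-defined adverse event categories also reach the split adverse event section.

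Much of this stands, and it is why the point is minor. It does not remove the point. No reason is given for treating laboratory values differently from ECGs. The adverse event route is only a partial substitute: changes enter it if judged clinically relevant (Protocol 5.2.2.1), and SAP Table 7.8.1: 1 has no lipid category. The 25 grade pairs in the working are table cells, not patients, and the eligibility limits rule some of them out. They do not rule out all: exclusion criterion 16 still admits Grade 1 hypokalaemia.

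Three stronger readings are tempting and not supported:
- A reader might infer that the REP runs from the last xentuzumab dose, so that arm 2 windows close by 9 December 2016 while arm 1 runs on. Protocol 5.2.2.2 explains why the length is 42 days, and SAP 6.3 derives a calendar date. Neither sets a start point, and SAP 7.8.1 points the other way.
- A reader might infer that baseline values distort the potential Hy's law screen, which uses "any on-treatment value of Alanine Aminotransferase (ALT) and/or Aspartate Transaminase (AST) > 3 Upper Limit of Normal (ULN) with total bilirubin" at or above twice ULN. An added value can only add a flagged case. Protocol 3.3.2 admits baseline transaminases above 3 times ULN only with liver metastases, and bilirubin above 1.5 times ULN only with Gilbert syndrome. The effect would be rare and over-inclusive.
- A reader might infer that toxicity is concealed. The worst grade over a longer window, or with baseline added, cannot be lower than without them.

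**Conclusion.** The point holds, at minor severity. As written, phase II laboratory outputs for arm 2 can combine xentuzumab-exposed values with later values on everolimus plus exemestane alone, and the adverse event part up to 9 December 2016 has no matching laboratory table. Read literally, the stand-alone worst-grade table and the worst-to-last transition can report a pre-treatment grade as the worst on-treatment grade, contrary to the SAP's own ECG definition.

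The size cannot be computed: last-dose dates, the snapshot date and the amendment 3 sampling schedule are not in the documents. The 1 to 16 point range for the baseline effect rests wholly on assumed frequencies.

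The conclusion assumes that the REP runs from the last dose of any trial drug, that some laboratory values were collected after 9 December 2016, and that no unsupplied document overrides SAP 7.8.2.1. Only descriptive safety outputs are affected, and the count of patients worsening from baseline does not depend on the baseline rule.

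**What to change.** - For phase II, present laboratory outputs for values on or before 9 December 2016 as the comparison between arms, and show later values in separate tables or listings.
- Derive the worst grade, both in the stand-alone table and in the worst-to-last transition, from values after first dose, using the SAP 6.7.1 rule for same-day samples. Keep baseline as the reference in the transition tables.

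The cost is a short change to SAP 7.8.2.1 and two filters in the laboratory programs. The date is already defined for adverse events and ECGs. The downside is one extra set of descriptive tables; no data are dropped.

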7.8.2.2 Laboratory values of special interest

Hepatic enzyme elevations (potential Hy's law cases):

These are defined as those cases where a combination of all of the following events occurred: any on-treatment value of Alanine Aminotransferase (ALT) and/or Aspartate Transaminase (AST) > 3 Upper Limit of Normal (ULN) with total bilirubin ≥ 2 ULN and Alkaline Phosphatase (ALKP) < 2 ULN. The events can occur in any order, but must occur within 14 days of the previous event, i.e. the second event must occur within 14 days of the first event, and the third event must occur within 14 days of the second event, etc.

Patients with missing laboratory values for liver enzymes will be excluded from these analyses but will be presented separately in a listing. Tabulations of hepatic enzyme elevations and liver laboratory values (see Section 5.2.2.1 of the CTP), including flags of true Drug-Induced Liver Injury (DILI) cases, are created in accordance with the Food and Drug Administration (FDA) DILI guidance ([P09-12413](#)).

7.8.3 Vital signs

Only descriptive statistics are planned for this section of the report.

7.8.4 ECG

Newly emergent abnormalities will be recorded and analysed as AEs if judged clinically relevant by the investigator.

The ECG analyses will be performed using the ECG Set, except those concerning the relationship between plasma concentrations and ECG endpoints which will be based on the ECG-PK set. All analyses will be based on the centrally evaluated ECG data collected until the safety cut-off date of 9th December 2016. Centrally evaluated ECGs recorded after this date, will only be presented in listings.

Descriptive analyses (separate analysis of Phase Ib and Phase II parts)

Absolute values and change from baseline in QTcF interval, QT interval, heart rate, PR interval, and QRS complex will be summarized descriptively by initial treatment, cycle, day and planned time.

Frequency tables will be provided for all categorical endpoints including notable findings and qualitative ECG assessments. Frequencies of the increases in QTcF and QT intervals above thresholds such as 450 msec, 480 msec, and 500 msec between baseline and on-treatment values will be displayed in two-way shift tables by initial treatment.

Notable findings (occurring until the safety cut-off date) of patients in the TS who are excluded from the ECG Set will be listed in separate listings which will be presented in Section 15 of the CTR.

The QTcB interval as well as the percentage changes for PR interval and QRS complex will only be displayed in Listings (Appendix 16.2.8)

Additional statistical analyses will be performed for the Phase II part as described below:

Repeated measures analyses

The endpoint 'change in QTcF interval between baseline and on-treatment' will be analysed by a linear mixed-effects model for repeated measures (MMRM). This model will include the fixed, categorical effects of 'treatment' and 'timepoint', the 'treatment-by- timepoint' interaction, as well as the continuous, fixed covariate 'baseline' and the 'baseline-by- timepoint' interaction. An unstructured covariance structure will be used to model the within-patient measurements. The SAS® procedure MIXED will be used, involving the restricted maximum likelihood estimation method, and the Kenward-Roger method will be applied to adjust standard errors and estimate denominator degrees of freedom. The model is detailed in [Section 9.2.2](#).

Timepoints will only be included as long as evaluable data in 'change in QTcF between baseline and on-treatment' from at least 30 patients are still available in any of the treatment groups. The choice of 30 patients is relatively arbitrary and is conceived as a compromise, i.e. balancing out between precision of the estimates and receiving preliminary information over time on the other hand. The analyses of heart rate, QT, PR and QRS endpoints will be aligned to the respective QTcF analyses.

For the pairwise comparisons of 'xentuzumab + everolimus+exemestane' versus 'everolimus+exemestane', the treatment differences at each timepoint will be estimated by the difference in the corresponding Least-Squares Means (LSMeans). Two-sided 90% CIs

Proprietary confidential information © 2018 Boehringer Ingelheim International GmbH or one or more of its affiliated companies

based on the t-distribution will also be computed. Having estimated the treatment difference at each timepoint by the analysis described above, the timepoint at which the difference is largest will be identified.

This analysis will also be performed using the corresponding endpoints based on the QT interval, heart rate, PR interval and QRS complex, respectively.

The repeated-measures analysis will also be applied to the absolute on-treatment QTcF interval, heart rate, QT interval, PR interval and QRS complex values, respectively. Least squares means of ‘treatment-by-timepoint’ and two-sided 95% CIs based on the t-distribution will be computed.

Sensitivity analysis

In the model described above, a covariance structure of type ‘unstructured’ will be used to model the within-patient measurements. This model does not consider the particular underlying time structure, being consecutive pairs of within-day measurements (pre- and post-dose measurements approximately 1 hour apart) separated by one (or more) week(s). To account for this particular time structure, a modified covariance structure will be used in the sensitivity analysis: A two-by-two unstructured covariance matrix will be used to model the within-patient measurements on each day (pre- and post-dose measurements). A second two-by-two unstructured covariance matrix will be used to model the within-patient measurements between days; this matrix will be the same for all combinations of days. Hence, in this analysis the number of necessary covariance parameter estimates will not depend on the number of included timepoints. The sensitivity analysis will be restricted to the endpoints based on the QTcF interval. The model is detailed in [Section 9.2.2](#).

Exposure-response analyses

The exposure-response analyses will be based on the ECG-PK set. Patients of the Phase Ib part will not be included as they were pre-treated with ‘everolimus+exemestane’. Data of patients receiving everolimus+exemestane alone will be included with xentuzumab plasma concentrations set to zero (see also [R17-0553](#)).

Pairs of xentuzumab plasma concentrations and QTcF changes from baseline that are not time-matched (i.e. a time deviation between PK blood sampling and ECG recording that is not acceptable) will be excluded from the analyses.

The maximum acceptable time deviations between PK blood sampling and ECG recording at different time points during the trial are presented in [Table 7.8.4: 1](#) below. Pairs of plasma concentrations and QTc changes from baseline with time deviations exceeding those specified in the table will be excluded from exposure-response analyses. When the sampling time of the blood sample, the time of ECG recording or the time of infusion are not available, the pair will also be excluded.

Proprietary confidential information © 2018 Boehringer Ingelheim International GmbH or one or more of its affiliated companies

Table 7.8.4: 1 Maximum acceptable time deviations between PK blood sampling and ECG recording during the trial, Phase II part

Timepoint	Pre-dose timepoints	Post-dose timepoints
	Both measurements taken before “start of infusion”	Both measurements taken not earlier than 15 min before “end of infusion”
Cycle 1, Day 1	n.a. (Baseline ECG)	Deviation \leq 4 h
Cycle 1, Day 8, 15	Deviation \leq 6 h	Deviation \leq 4 h
Cycles 2 and 3, Day 1		
Cycles >3, Day 1	Deviation \leq 6 h	n.a.
EoT, FU	(no infusion)	Deviation \leq 8 h

For further details see also [Section 6.6.5](#).

The relationship between xentuzumab plasma concentrations and QTcF change from baseline will be explored using a random coefficient model including a categorical variable ‘treatment’ with the two levels ‘xentuzumab+ everolimus+exemestane and ‘everolimus+exemestane’ to estimate the adjusted mean difference between ‘xentuzumab + everolimus+exemestane’ and ‘everolimus+exemestane’ in QTcF change from baseline and its two-sided 90% CI at clinically relevant plasma concentrations, which are the geometric means of the C1D1_{1:15h}, C2D1_{1:15h} and C3D1_{1:15h} values of the RP2D. The model is detailed in [Section 9.2.3](#). For visualization, plasma concentration against QTcF changes from baseline will be plotted, as well as the (fixed effect) regression line, its 90% CI and the geometric means of C1D1_{1:15h}, C2D1_{1:15h} and C3D1_{1:15h}.

The assumption of a linear relationship will be checked by visual inspection of diagnostic plots (presented in Section 16.1.9.2 of the CTR). If linearity is not given, the concentrations may be log-transformed prior to the analysis.

To inspect (graphically) whether the peaks of the time-profiles for xentuzumab plasma concentrations and QTcF interval changes from baseline coincide, figures of the individual time profiles of xentuzumab plasma concentrations and QTcF interval changes from baseline will be generated for each patient (presented in Appendix 16.1.9.2 of the CTR), as well as for the means (presented in Section 15 of the CTR). Mean time profiles from the patients treated with ‘everolimus+exemestane’ alone will be displayed as well.

[figure not shown]
These analyses will also be performed using the corresponding endpoints based on the QT interval and heart rate.

Furthermore, a first sensitivity analysis will be performed using the random coefficient model described above including the categorical effect ‘day’, and a second sensitivity analysis will be done including the categorical effect ‘time’ with the two levels pre- and post-dose, instead. A further analysis will consider the influence of baseline and will include the centered baseline as a covariate additionally to the factors used in the first sensitivity analysis. These analyses will only be applied to the QTcF changes from baseline.

Proprietary confidential information © 2018 Boehringer Ingelheim International GmbH or one or more of its affiliated companies

Appropriateness of QT interval correction methods for heart rate

To evaluate the appropriateness of the methods, slopes of the relationship of QT, QTcF, and QTcB interval versus RR interval (values log-transformed using the natural logarithm) will be estimated by applying a random coefficient model (see [Section 9.2.4](#)) separately for the treatments ‘xentuzumab+ everolimus+exemestane’ and ‘everolimus+exemestane’. These analyses will be based on the three single on-treatment ECG recordings per time point. A table of the resulting (fixed effect) slopes will be displayed together with two-sided 95% CIs in Appendix 16.1.9.2 of the CTR.

